10.8 Criteria for Taking a Patient Off Study

Patients will be recorded at the time of death from any cause, and depending upon cause, may contribute to an invasive cancer event. Date and cause of death will be recorded. Patients lost to follow up will be defined as those patients for whom clinical data is not available for ≥ 24 months. Those patients will be censored at 24 months from last contact.

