10.2 Sample Size, Accrual Time and Study Duration

Power and Sample Size Considerations. Sample size for this study was estimated using a 2-group test of non-inferiority of proportions, with the 2-year invasive breast cancer rate in the surgery group assumed to be 0.10 based on published studies.^{61,62} The non-inferiority margin assumed was 0.05. Based on a 1-sided un-pooled z-test, with alpha=0.05, a sample size of n=446 per group will have 80% power⁶⁴ to detect the specified non-inferiority margin. The proportion of patients who decline the arm to which they are specifically randomized can diminish the estimate of treatment difference, and could also widen the confidence bounds, but the analytical approaches proposed here aim to diminish the impact on bias of the treatment difference. With a 3-year duration of accrual and 2 additional years of follow-up, we anticipate approximately 148 total events.

Analysis of Primary Outcome (See below for outcomes definitions). This trial was designed anticipating non-acceptance of arm allocation, and the proportion of patients that do not accept their arm allocation can lead to bias in estimates of treatment differences. Thus, we plan to complete several analyses of the primary outcome, reporting the primary intent to treat (ITT) analysis as well as sensitivity analyses that are intended to reduce the bias in estimation of treatment difference in this setting.

We assume that a clinically acceptable difference in 2-year invasive cancer diagnosis rate in order to conclude non-inferiority is 5%. Cumulative incidence curves will be used to estimate the invasive cancer diagnosis rates over time, and at the 2-year point, the difference in rates will be estimated and a 1-sided upper confidence bound of (AM-GCC) will be computed, using methods described by Austin.⁶⁵ We will conclude that AM is not inferior to Surgery if the upper confidence bound on the risk difference at 2 years is less than 5%.

ITT Analysis. The ITT analysis of 2-year invasive cancer diagnosis rate will be conducted using all patients, as randomized, and will be completed using Kaplan-Meier estimates, stratified by group, combined with the Greenwood's confidence interval. The difference in invasive cancer risks will be computed from the Cox model with treatment at 2 years, with a 1-sided 95% confidence interval of the difference (AM-GCC) computed.

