10.7 Survival Follow up

Any study participant can choose to withdraw from the study at any time for any reason, including no specified reason. Patients in the surgery arm cannot opt for the AM arm after surgery, but in the event that a patient withdraws from the study, the date of withdrawal and reason for withdrawal will be recorded. The patient will be censored in time-to-event analyses at the date of withdrawal from the study

Patients in the AM arm may choose to either withdraw from the study or opt to proceed with surgery at any time. In the event that a patient in the AM arm opts to proceed with surgery in the absence of invasive progression, the date of withdrawal and reason for withdrawal will be recorded. As for the surgery arm, in the event that a patient withdraws from the study, the patient will be censored at the date of withdrawal from the study.

Patients in the AM arm with progression to invasive breast cancer are required by the study protocol to proceed with surgery for their invasive breast cancer. Patients who have invasive breast progression and do not wish to have surgery will continue to remain in follow up with their invasive cancer event recorded, at the time of invasive breast progression for the primary analysis. For further exploratory analyses, the lack of surgery for these patients will be recorded.

For patients who choose to no longer be followed per the protocol schedule, the patient can choose to enter the Survival Follow-up Phase. Survival data, ongoing adjuvant therapies and subsequent disease progression data will be collected during this phase of the study every 12 months for 10 years from registration. Telephone contact is acceptable as well as medical record review.

Follow-up will be discontinued early due to:

- Patient Death
- Patient Withdrawal of consent for all follow-up
- Patient deemed lost to follow-up

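### Patients lost to follow-up are censored 24 months after last contact, so those last seen before month 24 count as cancer-free for the whole 2-year primary window

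*Combined protocol and SAP*

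**What the plan says.** Section 10.8 gives the definition: "Patients lost to follow up will be defined as those patients for whom clinical data is not available for ≥ 24 months". The next sentence dates the censoring: "Those patients will be censored at 24 months from last contact".

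The footnotes to Table 1 (Section 7) count time points from registration. Section 10.2 concludes that "AM is not inferior to Surgery if the upper confidence bound on the risk difference at 2 years is less than 5" per cent. The same section describes the intention-to-treat analysis in two ways: it is "completed using Kaplan-Meier estimates, stratified by group", with Greenwood intervals, and also "The difference in invasive cancer risks will be computed from the Cox model with treatment at 2 years".

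Withdrawals follow a different rule in Section 10.7: "The patient will be censored in time-to-event analyses at the date of withdrawal from the study". Table 3 lists loss to follow-up as a censoring event for all four outcomes but gives no date. Section 10.8 is therefore the only place that dates the censoring of lost patients.

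**The concern.** Censoring should end a patient's time at risk when her status stops being known. The rule in Section 10.8 adds 24 months to that point, and 24 months is exactly the length of the primary window. Every patient it reaches who was last seen before month 24 is treated as if she had been followed and found free of cancer to 2 years.

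The effect on the comparison depends on when cancers are found. Section 2.1 describes the 10% surgery-arm rate as upstaging found at operation, and Section 5.1.2.1 expects surgery within 60 days, so few surgery-arm events come late enough to be hidden. AM events surface over two years of 6-monthly mammograms and are more exposed. With similar loss in both arms, the AM-minus-surgery difference shrinks, which in a non-inferiority trial is the unsafe direction.

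**Working it through.** **The plan's own figure.** For 10% v 10%, margin 5 points, one-sided alpha 0.05 and 80% power, unpooled: n = 2 × 0.09 × (1.645 + 0.842)² / 0.05² = 445.1, so 446 per group as stated. The planned size is not in dispute.

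**The date.** A patient last seen event-free at month t < 24 is censored at t + 24 ≥ 24. She contributes 24 − t unobserved months as event-free. This needs no assumption.

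**Inputs for the size.** From the documents: surgery rate 10% and margin 5 points (10.2), so 15% in AM is the boundary case; 1,080 patients 1:1, so 540 per arm. Assumed: loss of 2%, 5% or 10% by month 24, equal in both arms and uniform over months 0–24, with every such loss meeting the definition. Three assumed timing patterns:

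- A: constant hazard in both arms (mean event month 11.7 AM, 11.8 surgery).
- B: AM as in A; surgery events mostly at operation (mean 0.9 × 1.5 + 0.1 × 15 = 2.85).
- C: surgery as in B; AM events at months 6, 12, 18 and 24 (mean 15).

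**Formulas.** Under the rule the estimated 2-year risk is p × (1 − loss × mean event month / 24). Hidden events are 540 × p × loss × mean event month / 24. The chance of declaring non-inferiority is Φ((0.05 − 1.645 SE − RD) / SE), where RD is the risk difference.

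**Example (C, 5% loss).** AM: 0.15 × (1 − 0.05 × 15/24) = 14.53%. Surgery: 0.10 × (1 − 0.05 × 2.85/24) = 9.94%. RD = 4.59 points and SE = 1.99 points, so Φ(−1.44) = 7.5%.

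**All patterns.** The last column is a Kaplan-Meier/Greenwood simulation of 12,000 trials per cell, with both censoring dates applied to the same trials (Monte Carlo SE about 0.2–0.4 points).

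| Loss | RD, A / B / C (true 5.0) | False non-inferiority, formula, A / B / C | Simulated, rule v last-contact censoring, A; B; C |
|---|---|---|---|
| 2% | 4.95 / 4.88 / 4.84 | 5.3 / 5.7 / 5.9% | 5.5 v 5.3; 5.2 v 4.6; 6.1 v 5.0 |
| 5% | 4.88 / 4.69 / 4.59 | 5.7 / 6.8 / 7.5% | 6.0 v 5.5; 7.0 v 5.2; 7.6 v 5.2 |
| 10% | 4.76 / 4.39 / 4.18 | 6.4 / 9.1 / 10.9% | 6.4 v 5.0; 9.3 v 5.2; 11.0 v 5.2 |

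Hidden events at 5% loss: 2.0–2.5 of 81 in AM and 0.3–1.3 of 54 in surgery. At 10%: 3.9–5.1 and 0.6–2.7.

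**Only patients already silent for 24 months at the cut-off.** Assume uniform accrual and a cut-off 24 months after the last entry. The share of early losses meeting the definition is then 1 − 12/78 = 85% for the 78-month accrual in the synopsis. Section 10.2 instead plans "With a 3-year duration of accrual and 2 additional years of follow-up", which gives 1 − 12/36 = 67%. The simulated Kaplan-Meier error at 5% loss becomes 5.9–7.2% (85%) or 5.8–6.9% (67%); at 10% loss, 6.1–10.0% or 5.9–9.2%.

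**Cox reading** (treatment only, delta-method bound, range over two tie methods). With no loss the error is already 7.6–9.0% in B and 9.6–10.2% in C, because hazards are not proportional (A 5.2%). The censoring rule adds about 0.2–0.6 points at 2% loss, 0.6–1.3 at 5% and 1.5–2.8 at 10%.

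**Reversal.** At 5% base loss (Kaplan-Meier), extra loss at entry confined to the surgery arm restores RD to 5.0 when it reaches 3.1 points (B) or 4.1 points (C). Beyond that the bias runs against AM.

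**The case against.** The strongest case concerns size, not wording. The documents state no loss rate, and the rule reaches a narrow group. Withdrawals have their own date. Missed mammograms prompt a telephone call (6.1.2). For patients who leave the visit schedule, "Telephone contact is acceptable as well as medical record review". If only 1% per arm were lost in this way, the formula gives 5.1–5.4%, which is negligible; at 2% loss the simulated contrast in pattern A cannot be told from noise. Patterns B and C also ignore crossover, which Section 10.2 expects and which pulls the two arms' timing together. If 25% of events in each arm followed the other arm's timing (an assumption), the 5%-loss figures fall to 6.1% (B) and 6.4% (C), and the 10%-loss figures to 7.3% and 8.2%. All of this stands and limits the magnitude.

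It can also be said that the sentence is loose wording for last contact, and that Section 10.2 plans inverse probability weighting, latent class models and simulations for loss. Neither removes the defect. The sentence states an explicit date; if another was meant, it needs correcting anyway. The planned sensitivity work may expose the distortion but does not reset the date in the intention-to-treat analysis.

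Last, mammography of the affected breast is 6-monthly in AM and 12-monthly in surgery, so a date based on last documented status could differ by arm. Clinical examination is 6-monthly in both arms during years 1–5, which makes this minor.

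**Conclusion.** The concern holds. As written, the censoring rule counts unobserved time as cancer-free through the primary window, and no other section corrects it. That conclusion rests on the text alone.

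The size is conditional on the assumed loss and event timing. The effect is minor at 1–2% loss and material for a 5% one-sided test if 5–10% of each arm is lost in this way and the difference comes from Kaplan-Meier. It is smaller under the Cox reading, with crossover, or when only patients already silent for 24 months are carried forward. The likely direction is towards non-inferiority. The shift is small if event timing is similar in the two arms. This should be fixed before the primary analysis.

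**What to change.** Replace the censoring sentence in Section 10.8 with: *For the invasive-cancer endpoint, patients lost to follow-up are censored at the last date on which their invasive-cancer status was documented (clinic visit, breast imaging, pathology, or the telephone or medical-record follow-up that the protocol accepts).*

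Keep the 24-month gap only as the trigger for declaring loss. Apply the same date to patients out of contact for less than 24 months at the data cut-off, for whom the plan now states none, and in all sensitivity analyses. Add the date to Table 3, leave the withdrawal rule in Section 10.7 as it is, and report loss by arm.

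The cost is one sentence and a table note. The visit, imaging, pathology and telephone or record-review data are already collected. The standard error rises slightly, and loss is still assumed to be non-informative, which the Section 10.2 sensitivity analyses should probe. The change does not settle whether Kaplan-Meier or Cox supplies the primary difference. That choice needs its own decision, because under Cox the error in patterns B and C stays at 9.0–12.6% (5% loss) and 10.7–15.9% (10% loss) even with last-contact censoring.

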10.9 Study Monitoring (Reports, Summaries)

Enrollment and AE/SAE reports will be completed every 6 months from study initiation and submitted to the AFT office and the DSMB.

10.10 Data and Safety Monitoring

Interim Reports from the statistical team will be generated for the Data and Safety Monitoring Board (DSMB), as per the safety monitoring plan.

11 GENERAL REGULATORY CONSIDERATIONS AND CREDENTIALING (ETHICAL CONSIDERATIONS AND ADMINISTRATIVE PROCEDURES)

11.1. Compliance with Trial Enrollment and Results Posting Requirements

The trial and its results are subject to the requirements for submission to the Clinical Trials Data Bank, <http://www.clinicaltrials.gov>. Information posted will allow patients to identify potentially appropriate trials for their health-related conditions and pursue participation by calling a central contact number for further information on appropriate trial locations and trial site contact information.

11.2. Regulatory and Ethical Compliance

By signing the protocol, the investigator agrees to treat all of the information that is provided with the strictest confidentiality and to require the same of his/her personnel as well as the IRB. Study documents (protocols, investigator's brochures, eCRFs, etc.) provided by the AFT will be stored in an appropriate manner in order to ensure confidentiality. The information provided to the investigator by AFT must not be made available to other parties without a direct written authorization by the aforesaid parties, with the exception of the extent to which disclosure is necessary in order to obtain informed consent from the patients who wish to participate in the study.

This study will be conducted in compliance with the study protocol, subsequent amendment(s) and with the study-specific manuals/guidelines, if applicable. These documents ensure that the ICH E6 guideline for Good Clinical Practice is maintained as well as compliance with the principles of the Declaration of Helsinki (World Medical Association), or the laws and regulations of the country in which the research is conducted, whichever afford the greater protection to the individual. The study will comply with the requirements of the ICH E2A guideline (Clinical Safety Data Management: Definitions and Standards for Expedited Reporting).

By signing the study protocol the investigator agrees to comply with the instructions and procedures described therein and thus to adhere to the principles of good clinical practice, which these instructions and procedures reflect.

11.3. Informed Consent

If potential participants wish to speak with a patient advocate about the trial or any other aspect of the study, they will be provided with the contact details of a member of the COMET Patient Leadership Team (PLT). All participants (both potential and registered) will be provided with access to educational materials specifically designed by the PLT to inform them about the study, as well as to support decision making between options allowed in each arm following randomization.

It is the responsibility of the Investigator, or a person designated by the Investigator (if acceptable by local regulations), to obtain written Informed Consent from each patient participating in this study, after adequate explanation of the aims, methods, anticipated benefits, and potential hazards of the study. This information must be provided to the patient prior to undertaking any trial-related procedure which is not part of the routine clinical management of the patient (i.e. would not be indicated outside the study).

It is the investigator's responsibility to obtain the signed Informed Consent Form, and a signature from the person conducting the informed consent discussion, prior to undertaking any trial-related procedure. The proposed Informed Consent Form must comply with the ICH GCP guideline and regulatory requirements

11.4. Responsibilities of the Investigator/IRB/IEC/REB

The regulatory requirements for the Investigator can be found in Subpart D of 21CFR312(21CFR 312.60: General Responsibilities of Investigators) and in ICH E6 Section 4.

Additional requirements are also outlined in the Statement of Investigator Responsibilities (Form FDA 1572) and the Site Services Agreement. Alliance Foundation Trials, LLC (AFT) will supply the protocol and subsequent amendments.

The Investigator is responsible for ensuring all patients are informed about the study and that written consent is obtained prior to the conduct of any study related procedures. In addition, the Investigator is responsible for reviewing all health-related information collected for each study patient in order to identify any safety related issues/adverse events (AE).

As specified in 21CFR 312.62 (Investigator Record Keeping and Record Retention) and ICH E6 Sections 4.9 and 8, the Investigator is responsible for ensuring that their study staff maintains and retains all study related documentation, including but not limited to: signed Informed Consent forms, medical records that are applicable for this study and source documents, the protocol, Institutional Review Board (IRB) approvals, relevant IRB and Sponsor correspondence, and assorted regulatory documents. The Investigator is responsible for retaining and keeping safe all patient related documentation. In order to do this, the site staff will complete electronic case report forms (eCRFs) (see Appendix 1) in a timely manner. Due to the limited nature of the study protocol signature pages, medical licenses, IRB member lists and regulatory documents including GCP and CVs for the Sub-Investigators will not be collected.

11.5. Protocol Deviations

The investigator is responsible to document and explain any deviations from the approved protocol. The investigator should promptly report any deviations that might impact patient safety and data integrity to AFT and if locally applicable, to the respective IRB in accordance with local IRB policies and procedures.

A deviation is a departure from the protocol. If deviations are discovered by the data manager, other member of study staff or otherwise, they will be discussed with the Investigator and study staff.

11.6. Protocol Amendments

Any modifications to the protocol or the Informed Consent Form which may impact on the conduct of the study, potential benefit of the study, or may affect patient safety, including changes of study objectives, study design, patient population, sample sizes, study procedures, or significant administrative aspects will require a formal amendment to the protocol. Such amendment will be released by AFT, agreed by the investigator(s) and approved by relevant IRBs prior to implementation. A signed and dated statement that the protocol, any subsequent relevant amended documents and the Informed Consent Form have been approved by relevant IRBs must be provided to AFT before the study is initiated.

Administrative changes of the protocol are minor corrections and/or clarifications that have no effect on the way the study is to be conducted. These administrative changes will be released by the AFT, agreed by the investigator(s) and notified to the IRB.

11.7. Retention of Records (Study Documentation, record keeping, and retention of records)

Any records and documents relating to the conduct of this study and the distribution of ICFs, eCRFs, PRO data, must be retained by the study chair until notification by AFT, or for the length of time required by relevant national or local health authorities, whichever is longer. After that period of time, the documents may be destroyed, subject to local regulations. No records may be disposed of without the written approval of AFT. Written notification should be provided to AFT prior to transferring any records to another party or moving them to another location.

11.8. Data Confidentiality

Patient medical information, both associated with biologic specimens or not, is confidential and may only be disclosed to third parties as permitted by the ICF (or separate authorization for use and disclosure of personal health information) which has been signed by the patient, unless permitted or required by law. Data derived from biologic specimen analysis on individual patients will in general not be provided to study investigators unless a request for research use is granted. The overall results of any research conducted using biologic specimens will be available in accordance with the effective AFT policy on study data publication.

11.9. Database Management and Quality Control

The Site Principal Investigator and/or his/her designee will prepare and maintain adequate and accurate participant case histories with observations and data pertinent to the study.

Rave EDC will be used for this study. The study data will be transcribed by study-site personnel from the source documents onto an eCRF, and transmitted in a secure manner to AFT within the timeframe agreed upon between the sponsor and the study site. The electronic file will be considered to be the eCRF.

The Clinical Research Coordinator (CRC) or designated study site personnel will complete the eCRF within 5 days following a subject visit and queries are to be addressed within 5 days from the date issued. Subjects will not be identified by name in the study database or on any study documents to be collected by the AFT (or designee), but will be identified by a site number, subject number.

In accordance with federal regulations, the Investigator is responsible for the accuracy and authenticity of all clinical and laboratory data entered onto ergs. Each eCRF must be reviewed for accuracy by the Investigator, corrected as necessary, and then approved.

At study completion, when the database has been declared to be complete and accurate, the database will be locked.

After data have been entered into the study database, a system of computerized data validation checks will be implemented and applied to the database on a regular basis. After upload of the data into the clinical study database they will be verified for accuracy and consistency with the data sources. Queries are entered, tracked, and resolved through the EDC system directly. The study database will be updated in accordance with the resolved queries. All changes to the study database will be documented.

At critical junctures of the protocol (e.g., production of interim and final reports), data for analysis is locked and cleaned per established procedures.

If the Investigator becomes unable for any reason to continue to retain study records for the required period (eg, retirement, relocation), AFT should be prospectively notified. The study records must be transferred to a designee acceptable to AFT, such as another investigator, another institution, or to AFT itself. The Investigator must obtain AFT's written permission before disposing of any records, even if retention requirements have been met.

